### Pembrolizumab

The planned dose and dosing interval of pembrolizumab for this study is 200 mg every 3 weeks (Q3W). Based on the totality of data generated in the Keytruda development program, 200 mg Q3W is the appropriate dose of pembrolizumab for adults across all indications and regardless of tumor types.

No pembrolizumab dose modifications are planned for this study.

# 6. Study Population

Male and female participants of at least 18 years of age, with selected advanced/metastatic solid tumors (NSCLC [PD-(L)1 refractory], CRPC, and MSS CRC) will be enrolled in this study.

Prospective approval of protocol deviations to recruitment and enrollment criteria, also known as protocol waivers or exemptions, is not permitted.

#### **Inclusion Criteria** 6.1

Participants are eligible to be included in the study only if all of the following criteria apply:

# Type of Participant and Disease Characteristics – All Participants

- 1. Have one of the following histologically- or cytologically-confirmed advanced/metastatic (diagnosis of Stage IV [AJCC version 8 or current version as applicable]) solid tumors (NSCLC, CRPC, or MSS CRC) by pathology report and have received, or been intolerant to, or have been ineligible for all treatment known to confer clinical benefit.
- 2. Have Stage III or Stage IV disease that is not surgically resectable.
- 3. Have measureable disease by RECIST 1.1 criteria as assessed by the local site investigator/radiology. Lesions situated in a previously irradiated area are considered measureable if progression has been demonstrated in such lesions.
- 4. Have supplied tumor tissue from either a newly obtained biopsy or an archival specimen from a site not previously irradiated for biomarker analysis.

**Product:** MK-7123 SCH 527123 46

**Protocol/Amendment No.:** 034-01

# Non-small cell lung cancer (NSCLC) Participants Only

5. Have a histologically or cytologically confirmed diagnosis of Stage IV metastatic NSCLC.

- 6. Stage IV metastatic NSCLC tumors that are PD-(L)1 positive (TPS  $\geq$ 50%), do not harbor EGFR-sensitizing mutations and ALK translocations that are amenable to treatment with respective tyrosine kinase inhibitor therapy, and who have received prior treatment with a PD-(L)1 antagonist
- 7. Must have progressed on treatment with an anti-PD-(L)1 monoclonal antibody (mAb) administered either as monotherapy, or in combination with other checkpoint inhibitors or other therapies. PD-1 treatment progression is defined by meeting all of the following criteria:
  - a. Has received at least 2 doses of an approved anti-PD-(L)1 mAb.
  - b. Has demonstrated disease progression after anti-PD-(L)1 as defined by RECIST 1.1 The initial evidence of disease progression (PD) is to be confirmed by a second assessment no less than 4 weeks from the date of the first documentation of PD in the absence of rapid clinical progression. (This determination will have been made by the investigator. Once PD is confirmed, the initial date of PD documentation will be considered the date of disease progression).
  - c. Progressive disease has been documented within 12 weeks from the last dose of anti-PD-(L)1 mAb.

# Castration Resistant Prostate Cancer (CRPC) Participants Only

- 8. Have histologically- or cytologically-confirmed (if acceptable according to local health authority regulations) adenocarcinoma of the prostate. Components of small cell prostate cancer are permitted. Diagnosis must be stated in a pathology report and confirmed by the investigator.
- 9. Have prostate cancer progression on the most recent treatment, as determined by the investigator, by means of one of the following:
  - a. PSA progression using local laboratory values as defined by a minimum of 2 rising PSA levels with an interval of  $\geq 1$  week between each assessment where the PSA value at screening should be ≥2 ng/mL
  - b. Radiographic disease progression in soft tissue based on RECIST 1.1 criteria with or without PSA progression.
  - c. Radiographic disease progression in bone defined as the appearance of 2 or more new bone lesions on bone scan with or without PSA progression.
    - Note: Radiographs must be collected and transmitted to the central imaging vendor at study entry.

- 10. Must have progressed on at least one second generation anti-androgen therapy (e.g., enzalutamide, abiraterone) according to PCWG3 guidelines.
- 11. Have ongoing androgen deprivation with serum testosterone <50 ng/dL (<2.0 nM).
  - a. If the participant is currently being treated with luteinizing hormone-releasing hormone agonists or antagonists (participants who have not undergone an orchiectomy), this therapy must have been initiated at least 4 weeks prior to first dose of trial treatment and treatment must be continued throughout the study.

# Microsatellite Stable Colorectal Cancer (MSS-CRC) Participants Only

- 12. Have a histologically proven locally advanced unresectable or metastatic (Stage IV) CRC.
- 13. Have locally confirmed microsatellite stable (MSS) CRC; participants with microsatellite instability-high (MSI-H) or microsatellite unstable CRC are not eligible.
- 14. Have been previously treated with standard therapies, which must include fluoropyrimidine, oxaliplatin, and irinotecan.
  - a. Participants who have withdrawn from standard treatment due to unacceptable toxicity warranting discontinuation of that treatment and precluding retreatment with the same agent before progression of disease will also be eligible.
  - b. Regimens given with adjuvant intent will be counted as treatment for metastatic disease if the participant's disease had progressed within 6 months following treatment.

## **Demographics – All Participants**

- 15. Men and women who are  $\geq$ 18 years of age.
- 16. Have an ECOG performance status of 0 or 1.

### Male participants:

17. A male participant must agree to use contraception as detailed in Appendix 3 of this protocol during the treatment period and for at least 120 days after the last dose of study treatment and refrain from donating sperm during this period.

# Female participants:

- 18. A female participant is eligible to participate if she is not pregnant (see Appendix 3), not breastfeeding, and at least one of the following conditions applies:
  - a.) Not a woman of childbearing potential (WOCBP) as defined in Appendix 3 OR
  - b.) A WOCBP who agrees to follow the contraceptive guidance in Appendix 3 during the treatment period and for at least 120 days after the last dose of study treatment.

### **Informed Consent**

19. The participant (or legally acceptable representative if applicable) provides written informed consent/assent for the study. The participant may also provide consent/assent for Future Biomedical Research. However the participant may participate in the main study without participating in Future Biomedical Research.

# **Laboratory Values – All Participants**

20. Demonstrate adequate organ function as defined by the following table (Table 1).

Table 1 Adequate Organ Function Laboratory Values

System	Laboratory Value
Hematological	Education value
Absolute neutrophil count	>1,500/mcL
Platelets a	>1,300/mcL >100,000/mcL
Hemoglobin a	≥9 g/dL or ≥5.6 mmol/L
Renal	27 g/dL 01 23.0 mmol/L
Serum creatinine or creatinine clearance (CrCl) (measured or calculated) or Glomerular Filtration Rate (GFR) in place of CrCl	≤1.5 X upper limit of normal (ULN) or ≥60 mL/min for participant with creatinine levels >1.5 X ULN
Hepatic	•
Total bilirubin	≤1.5 X ULN or Direct bilirubin ≤1.5 X ULN for participants with total bilirubin levels >1.5 X ULN; if there is no institutional ULN, then direct bilirubin must be <40% of total bilirubin to be eligible. Note: In no case can the total bilirubin exceed 3 X ULN.
Aspartate aminotransferase (AST) and Alanine aminotransferase (ALT)	≤2.5 X ULN or ≤5 X ULN for participants with liver metastases
Coagulation	
International Normalized Ratio (INR) or Prothrombin Time (PT)	≤1.5 X ULN unless participant is receiving anticoagulant therapy
Activated Partial Thromboplastin Time (aPTT) or Partial Thromboplastin Time (PTT)	≤1.5 X ULN unless participant is receiving anticoagulant therapy as long as PT or aPTT is within therapeutic range of intended use of anticoagulants

Protocol/Amendment No.: 034-01

**Product:** MK-7123 SCH 527123 49

Laboratory Value System

Note: This table includes eligibility-defining laboratory value requirements for treatment; laboratory value requirements should be adapted according to local regulations and guidelines for the administration of specific chemotherapies.

#### 6.2 **Exclusion Criteria**

Participants are excluded from the study if any of the following criteria apply:

### **Medical Conditions**

- 1. Has a known additional malignancy that is progressing or has required active treatment within the past 2 years.
  - Note: Participants with basal cell carcinoma of the skin, squamous cell carcinoma of the skin, or carcinoma in situ (eg, breast carcinoma, cervical cancer in situ) that have undergone potentially curative therapy are not excluded.
- 2. Has known active CNS metastases and/or carcinomatous meningitis. Participants with previously treated brain metastases may participate provided they are radiologically stable, ie, without evidence of progression for at least 4 weeks by repeat imaging (note that the repeat imaging should be performed during study screening), clinically stable and without requirement of steroid treatment for at least 14 days prior to first dose of study treatment.
- 3. Has had a severe hypersensitivity reaction to treatment with any monoclonal antibody or components of the study drug(s).
- 4. Has an active autoimmune disease that has required systemic treatment in the past 2 years (ie, with use of disease-modifying agents, corticosteroids, or immunosuppressive drugs) except vitiligo or resolved childhood asthma/atopy. Replacement therapy, such as thyroxine, insulin, or physiologic corticosteroid replacement therapy for adrenal or pituitary insufficiency, is not considered a form of systemic treatment and is allowed. Use of nonsystemic steroids is permitted. In addition to active autoimmune disease, participants who have previously been permanently discontinued from PD-(L)1 therapy due to immune related side effects are not eligible for the study.
- 5. Has an active infection requiring systemic therapy.
- 6. Has symptomatic ascites or pleural effusion. A participant who is clinically stable following treatment for these conditions (including therapeutic thoracocentesis or paracentesis) is eligible.
- 7. Has interstitial lung disease that required oral or intravenous glucocorticoids to assist with management.

04W5XD

<sup>a Criteria must be met without packed red blood cell (pRBC) transfusion within last 2 weeks. Participants can be on stable dose of erythropoietin (≥ approximately 3 months).

<sup>b Creatinine clearance (CrCl) should be calculated per institutional standard. If no local guideline is available, creatinine clearance should be calculated using the Cockcroft-Gault Method: CrCl = ([140-age] \* weight [kg] \* [0.85 for females only]) / (72 \* serum creatinine)

**Product:** MK-7123 SCH 527123 **Protocol/Amendment No.:** 034-01

- 8. Has a history of (non-infectious) pneumonitis that required steroids or has current pneumonitis.
- 9. Has undergone prior allogeneic hematopoietic stem cell transplantation within the last 5 years.
  - Note: Participants who have had a stem cell transplant >5 years ago are eligible as long as there are no symptoms of graft-versus-host disease (GVHD).
- 10. Has a known history of human immunodeficiency virus (HIV) infection.
  - Note: No HIV testing is required unless mandated by local health authority.
- 11. Has a known history of Hepatitis B (defined as Hepatitis B surface antigen [HBsAg] reactive) or known active Hepatitis C virus (defined as HCV RNA [qualitative] is detected) infection.
  - Note: No testing for Hepatitis B and Hepatitis C is required unless mandated by local health authority.
- 12. Has a history or current evidence of a gastrointestinal (GI) condition (eg, inflammatory bowel disease, Crohn's disease, ulcerative colitis) or impaired liver function or diseases that in the opinion of the Investigator may significantly alter the absorption or metabolism of oral medications; any condition, therapy, or laboratory abnormality that might confound the results of the study, interfere with the participant's participation for the full duration of the study, make administration of the study drugs hazardous, or make it difficult to monitor adverse effects such that it is not in the best interest of the participant to participate, in the opinion of the treating Investigator.
- 13. Has known psychiatric or substance abuse disorders that would interfere with the participant's ability to cooperate with the requirements of the study.
- 14. Is pregnant or expecting to conceive or father children within the projected duration of the study.
- 15. Has undergone major surgery and has not recovered adequately from any toxicity and/or complications from the intervention prior to starting study therapy.
- 16. A WOCBP who has a positive urine pregnancy test within 72 hours before the first dose of study treatment (see Appendix 3). If the urine test cannot be confirmed as negative, a serum pregnancy test is required. In such cases, the participant must be excluded from participation if the serum pregnancy result is positive.

# **Prior/Concomitant Therapy**

- 17. Participants with CRPC or MSS CRC who have received prior therapy with an anti-PD-1, anti-PD-(L)1, or anti PD L2 agent.
- 18. Have been treated with an agent directed to another stimulatory or co-inhibitory Tcell receptor (eg, CTLA-4, OX 40, CD137).

**Product:** MK-7123 SCH 527123 51

**Protocol/Amendment No.:** 034-01

19. Has received prior systemic anti-cancer therapy including investigational agents or has used an investigational device within 28 days prior to the first dose of study treatment. Note: Participants must have recovered from all AEs due to previous therapies to  $\leq$ Grade 1 or baseline. Participants with  $\leq$ Grade 2 neuropathy or alopecia may be eligible. Participants receiving ongoing replacement hormone therapy for endocrine immune-related adverse events (eg, thyroid replacement therapy) will not be excluded from participation in this study.

- 20. Has received prior radiotherapy (not to target lesions) within 2 weeks of start of study treatment. Participants must have recovered from all radiation-related toxicities, not require corticosteroids, and not have had radiation pneumonitis. A 1-week washout is permitted for palliative radiation (≤2 weeks of radiotherapy) to non-CNS disease.
- 21. Is expected to require any other form of antineoplastic therapy while on study.
- 22. Has a diagnosis of immunodeficiency or is receiving chronic systemic steroid therapy in excess of replacement doses (prednisone  $\leq 10 \text{ mg/day}$  is acceptable), or on any other form of immunosuppressive medication.

Note: The use of physiologic replacement doses of corticosteroids may be approved after consultation with the Sponsor Medical Monitor or designee.

23. Has received a live-virus vaccine within 30 days prior to first dose of study medication. Vaccines that do not contain live virus are permitted.

# **Prior/Concurrent Clinical Study Experience**

24. Had been previously treated with a CXCR2 inhibitor (eg, AZD5069, reparixin, danirixin, LY3041658 Ab, HuMax-IL8, etc.)

### 6.3 **Lifestyle Restrictions**

There are no lifestyle restrictions.

#### Screen Failures 6.4

Screen failures are defined as participants who consent to participate in the clinical study but are not subsequently randomized. A minimal set of screen failure information is required to ensure transparent reporting of screen failure participants to meet the Consolidated Standards of Reporting Trials (CONSORT) publishing requirements and to respond to queries from regulatory authorities. Minimal information includes demography, screen failure details, eligibility criteria, and any adverse events or serious adverse events (SAE) meeting reporting requirements as outlined in the data entry guidelines.

#### 6.5 **Participant Replacement Strategy**

A participant who discontinues from study treatment or withdraws from the study will not be replaced.

### 7. Treatments

Study treatment is defined as any investigational treatment(s), marketed product(s), placebo, or medical device(s) intended to be administered to a study participant according to the study protocol.

Clinical supplies [study treatment(s) provided by the Sponsor] will be packaged to support enrollment. Clinical supplies will be affixed with a clinical label in accordance with regulatory requirements.

#### 7.1 **Treatments Administered**

The study treatments to be used in this study are outlined below in Table 2 Study Treatment(s).

Study Treatment(s) Table 2

Study Treatment Name:	Navarixin (MK-7123)	Pembrolizumab (MK-3475)
Dosage Formulation:	Oral dry filled capsule	Solution for Infusion
Unit Dose Strength(s):	Two potencies: 10-mg and 50-mg capsules	100 mg/vial
Dosage Level(s):	30 mg QD 100 mg QD	200 mg Q3W
Route of Administration:	Oral	IV infusion
Sourcing:	Provided centrally by the Sponsor.	Provided centrally by the Sponsor.

All supplies indicated in Table 2 will be provided per the 'Sourcing' row depending upon local country operational requirements. Every attempt should be made to source these supplies from a single lot/batch number. The study site is responsible for recording the lot number, manufacturer, and expiry date for any locally purchased product as per local guidelines unless otherwise instructed by the Sponsor.

Refer to Section 9.1.8 for details regarding administration of the study treatment.

#### 7.2 **Dose Modification**

### 7.2.1 Navarixin Dose Modification

For Grade 4 ANC, or febrile neutropenia (Grade 3 or 4 ANC), navarixin will be held for 1 week to allow the ANC to recover. ANC will be measured for recovery at 1 week (local draw is permissible). If ANC has recovered to Grade 1 or better, the participant will be restarted at a lower dose of navarixin (ie, from 100 mg to 50 mg or from 30 mg to 20 mg), depending on the dose arm. If the participant has not recovered, he/she will return to the clinic in one week for a second ANC draw. If ANC has recovered to Grade 1 or better, the participant will be restarted at a lower dose of navarixin (ie, from 100 mg to 50 mg or from 30 mg to 20 mg), depending on the arm. If not recovered, he/she will discontinue navarixin, but remain on pembrolizumab treatment. There will only be one dose reduction per arm. If the participant experiences Grade 4 ANC or febrile neutropenia while already dosed reduced, the participant will discontinue navarixin treatment (Table 3).

For immune related AEs, see Section 7.2.2 for pembrolizumab dosing instructions. If pembrolizumab dosing is held, navarixin dosing should also be held. If pembrolizumab dosing is resumed, navarixin dosing may be restarted at a lower dose. If navarixin has already been dose reduced, then navarixin should be discontinued Table 3 and Section 7.2.2).

For DLTs (Section 5.1.3) not encompassed under irAEs (Section 7.2.2), both navarixin and pembrolizumab will be held for 1 week (an additional extension period for recovery of the toxicity may be allowed, following consultation with the Sponsor and the investigator). Then, if toxicity has recovered to Grade 1 or better (or participant's baseline value), participant will be restarted on the standard dose of pembrolizumab and a lower dose of navarixin (ie. from 100 mg to 50 mg or from 30 mg to 20 mg), depending on the dose arm. There will only be one navarixin dose reduction per arm. Therefore, if the participant experiences the DLT while already dosed reduced, the participant will discontinue navarixin, but may restart the standard dose of pembrolizumab following recovery (Table 3).

**Product:** MK-7123 SCH 527123 **Protocol/Amendment No.:** 034-01

Navarixin/Study Drug Dose Modifications Table 3

Toxicities	Navarixin Dosing	Action
Grade 4 ANC	Hold navarixin for 1 week for ANC to recover.	
 
If ANC recovered to Grade 1 or better, participant will be restarted at lower dose of navarixin (ie, from 100 mg to 50 mg or from 30 mg to 20 mg), depending on the arm.
 
If ANC has not recovered,
 

		participant will receive a second ANC test after an additional 1 week  If ANC recovered to Grade 1
		or better, participant will be restarted at lower dose of navarixin (ie, from 100 mg to 50 mg or from 30 mg to 20 mg), depending on the arm.
		
 
If ANC has not recovered, participant will discontinue navarixin treatment, but will continue to receive pembrolizumab treatment.
 

Febrile neutropenia (Grade 3 or 4 ANC)	Hold navarixin for 1 week for ANC to recover.	• If ANC recovered to Grade 1 or better, participant will be restarted at lower dose of navarixin (ie, from 100 mg to 50 mg or from 30 mg to 20 mg), depending on the arm.
		
 
If ANC has not recovered, participant will receive a second ANC test after an additional 1 week
 

		• If ANC recovered to Grade 1 or better, participant will be restarted at lower dose of navarixin (ie, from 100 mg to 50 mg or from 30 mg to 20 mg), depending on the arm.
		
 
If ANC has not recovered, participant will discontinue navarixin treatment, but will continue to receive pembrolizumab treatment.
 

Toxicities	Navarixin Dosing	Action
Grade 4 ANC or febrile neutropenia while navarixin already dosed reduced	There will be only 1 dose reduction per arm.	Participant will discontinue navarixin.
	Study Medication Dosing	
Immune related AEs (irAEs) which require pembrolizumab dose modification (See Section 7.2.2)	Follow Section 7.2.2 for pembrolizumab dosing instructions.  Hold navarixin while pembrolizumab is held to allow irAE to recover.	
 
Hold/discontinue pembrolizumab dosing according to instructions in Section 7.2.2
 
Hold navarixin while pembrolizumab is held.
 
If pembrolizumab is restarted, restart navarixin at lower dose of navarixin (ie, from 100 mg to 50 mg or from 30 mg to 20 mg), depending
 

		

on the arm.

If navarixin has already been dose reduced, discontinue navarixin.

DLTs not described above (see Section 5.1.3)	Hold navarixin for 1 week* for DLT to recover.  Hold pembrolizumab while navarixin is held.  *An additional extension period for recovery of the toxicity may be allowed, following consultation with the Sponsor and the Investigator.	
 
If toxicity has recovered to Grade 1 or better (or participant's baseline value), participant will be restarted at lower dose of navarixin (ie, from 100 mg to 50 mg or from 30 mg to 20 mg), depending on the arm. If navarixin has already been dose reduced, discontinue navarixin. Pembrolizumab will be restarted at normal dose.
 
If toxicity has not recovered, participant will discontinue study treatment (discontinue both pembrolizumab and navarixin).
 

**Product:** MK-7123 SCH 527123 56

**Protocol/Amendment No.:** 034-01

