## **Myocarditis:**

o For Grade 1 or 2 events, withhold. Based on severity of AE administer corticosteroids. Ensure adequate evaluation to confirm etiology and/or exclude other causes.

22-Mar-2018 Confidential 07WYDZ 04W5XD

> o For Grade 3 and 4 events, permanently discontinue. Based on severity of AE administer corticosteroids. Ensure adequate evaluation to confirm etiology and/or exclude other causes.

Management of Infusion Reactions: Signs and symptoms usually develop during or shortly after drug infusion and generally resolve completely within 24 hours of completion of infusion.

Table 5 shows treatment guidelines for participants who experience an infusion reaction associated with administration of pembrolizumab (MK-3475).

Pembrolizumab Infusion Reaction Treatment Guidelines Table 5

NCI CTCAE Grade	Treatment	Premedication at
		subsequent dosing
Grade 1	Increase monitoring of vital signs as	None
Mild reaction; infusion	medically indicated until the	
interruption not indicated;	participant is deemed medically	
intervention not indicated	stable in the opinion of the	
	investigator.	
Grade 2	Stop Infusion and monitor	Participant may be
Requires infusion	symptoms.	premedicated 1.5h (± 30
interruption but responds	Additional appropriate medical	minutes) prior to infusion
promptly to symptomatic	therapy may include but is not limited	of pembrolizumab (MK-
treatment (e.g.,	to:	3475) with:
antihistamines, NSAIDS,	IV fluids	Diphenhydramine 50 mg
narcotics, IV fluids);	Antihistamines	orally (or equivalent dose
prophylactic medications	NSAIDS	of antihistamine).
indicated for ≤24 hours	Acetaminophen	Acetaminophen 500-1000
	Narcotics	mg orally (or equivalent
	Increase monitoring of vital signs as	dose of antipyretic).
	medically indicated until the	
	participant is deemed medically	
	stable in the opinion of the	
	investigator.	
	If symptoms resolve within one hour	
	of stopping drug infusion, the	
	infusion may be restarted at 50% of	
	the original infusion rate (e.g., from	
	100 mL/hr to 50 mL/hr). Otherwise	
	dosing will be held until symptoms	
	resolve and the participant should be	
	premedicated for the next scheduled	
	dose.	
	Participants who develop Grade 2	
	toxicity despite adequate	
	premedication should be	
	permanently discontinued from	
	further trial treatment	
	administration.	

NCI CTCAE Grade	Treatment	Premedication at subsequent dosing
Grades 3 or 4	Stop Infusion.	No subsequent dosing
Grade 3:	Additional appropriate medical	

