Prolonged (i.e., not rapidly	therapy may include but is not limited	
responsive to symptomatic	to:	
medication and/or brief	IV fluids	
interruption of infusion);	Antihistamines	
recurrence of symptoms	NSAIDS	
following initial	Acetaminophen	
improvement;	Narcotics	
hospitalization indicated for	Oxygen	
other clinical sequelae (e.g.,	Pressors	
renal impairment,	Corticosteroids	
pulmonary infiltrates)	Epinephrine	
Grade 4:	Increase monitoring of vital signs as	
Life-threatening; pressor or	medically indicated until the	
ventilatory support	participant is deemed medically	
indicated	stable in the opinion of the	
	investigator.	
	Hospitalization may be indicated.	
	Participant is permanently	
	discontinued from further trial	
	treatment administration.	

Appropriate resuscitation equipment should be available in the room and a physician readily available during the period of drug administration.

**Product:** MK-7123 SCH 527123 **Protocol/Amendment No.:** 034-01

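### The DLT restart rule in Section 7.2.1 and Table 3 does not except infusion reactions, so for a related Grade 4 reaction in Cycle 1 it contradicts Table 5; re-dosing is unlikely, and one clause in two places removes the conflict

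*Combined protocol and SAP*

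**What the plan says.** Four places bear on the point.

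- **Section 5.1.3 (DLT definition).** A Cycle 1 toxicity judged related to study treatment is a DLT if it is a non-laboratory, non-hematologic Grade 4 event (item 1), or a Grade 3 event of that kind persisting beyond 3 days under optimal supportive care (item 5). The listed exceptions concern laboratory abnormalities. Infusion reactions are not excepted. Section 5.1.2 mentions one as an example when it sets DLT evaluability, so the event was foreseen.
- **Section 7.2.1, DLT paragraph.** It opens "For DLTs (Section 5.1.3) not encompassed under irAEs (Section 7.2.2"). Both drugs are held for 1 week, with a possible extension. If the toxicity is then Grade 1 or better, or back to baseline, the "participant will be restarted on the standard dose of pembrolizumab and a lower dose of navarixin".
- **Table 3, last row.** This row takes every DLT not covered by the rows above it, which deal with neutrophil events and immune-related AEs. After recovery navarixin is reduced and "Pembrolizumab will be restarted at normal dose".
- **Section 7.7.1, Table 5.** For a Grade 3 or 4 infusion reaction, the column on later dosing reads "No subsequent dosing". The treatment column ends "Participant is permanently" taken off trial treatment.

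**The concern.** One event falls under two rules with opposite instructions. The restart rule sits in the dose-modification section and is worded as a directive. The stopping rule sits in the supportive-care section. Section 7.7.1 refers the reader to Section 7.2 for dose modification, while 7.2.1 and Table 3 never refer to Table 5. A site that looks up what to do after a DLT could read only the restart rule.

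At stake is re-exposure of a participant to pembrolizumab after a life-threatening infusion reaction. This is a question of participant safety, not of inference.

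**Working it through.** The plan states no figure to reproduce, and no rate or sample size enters. The check is to follow one event through the text: a treatment-related Grade 4 pembrolizumab infusion reaction at the Cycle 1 Day 1 infusion.

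1. **Is it a DLT?** Yes, under item 1 of Section 5.1.3. It is Grade 4, non-hematologic, not a laboratory value, related, and in Cycle 1.
2. **Is it excepted as an immune-related AE?** Not by name. Table 4 does not list infusion reactions, and the protocol gives them a separate table.
3. **Is it in an earlier row of Table 3?** No. Those rows cover Grade 4 ANC, febrile neutropenia, their recurrence at a reduced dose, and immune-related AEs.
4. **Which branch of the restart rule applies?** Section 7.7.1 says reactions "generally resolve completely within 24 hours of completion of infusion". The hold is 1 week, or 7 × 24 = 168 hours. A reaction that follows the usual course will have recovered by then, so the branch reached is the restart, not the branch in Table 3 that stops both drugs for lack of recovery.
5. **What does Table 5 say?** No further dosing, and permanent discontinuation of trial treatment.
6. **Is precedence stated?** No. Neither rule refers to the other.

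The conflict at Grade 4 is therefore present in the wording. Two adjoining cases need separate treatment.

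- **Grade 3.** Under item 5 the reaction must last more than 3 days, which is 3 × 24 = 72 hours. That is 72 / 24 = 3 times the period within which reactions generally resolve. This case is nearly empty.
- **Participants already on reduced navarixin.** The last sentence of the 7.2.1 paragraph says such a participant "may restart the standard dose of pembrolizumab following recovery". Both drugs start on Cycle 1 Day 1, and a reduction can only follow a hold, so nobody is dose-reduced at that infusion. The sentence creates no conflict for a Cycle 1 Day 1 reaction.

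**The case against.** The strongest reply is that nobody would be re-dosed. Several parts of the protocol support it.

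- Table 5 is specific to the event and takes effect when the infusion is stopped. The restart step comes at least a week later, when the participant should already be off treatment.
- Its intent is plain from the Grade 2 row: "Participants who develop Grade 2" toxicity despite adequate premedication are also taken off treatment permanently. Exclusion criterion 3, which bars people with a prior severe hypersensitivity reaction to any monoclonal antibody or study-drug component, points the same way.
- Appendix 4 requires advance approval by the Sponsor Clinical Director before rechallenge after a serious, possibly related event. A life-threatening reaction is serious by definition.
- Section 8.1 requires discontinuation when continued treatment is judged to put the participant at unnecessary risk.
- Section 7.2.2 says AEs associated with pembrolizumab may be immunologic and may appear soon after the first dose. A site that classed the reaction as immune-related would reach Table 4's catch-all row, which stops pembrolizumab permanently at Grade 4, and the pembrolizumab conflict would not arise.

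All of this stands, and it is why the point is minor. It does not remove the contradiction. The rechallenge note says approval follows the protocol's dose-modification guidelines, which leads back to the section containing the restart rule. The immune-related route depends on a classification that the protocol does not state.

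A reader might go further and infer that the protocol intends rechallenge after Grade 4 reactions, that the sentence on dose-reduced participants is a second live conflict, or that the number of exposed infusions can be counted. The documents support none of these. Table 5 contradicts the first, and the start of both drugs on the same day rules out the second for the Day 1 infusion. A count would depend on whether 7.2.1 uses the term DLT only for Cycle 1. Section 5.1 applies the definition outside that window, though only for a stopping rule.

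**Conclusion.** The contradiction is real but narrow. It concerns a related Grade 4 infusion reaction in Cycle 1, for which the DLT paragraph of 7.2.1 and the last row of Table 3 give an instruction that is wrong as written and opposite to Table 5. The Grade 3 case is all but empty.

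The conclusion rests on two readings: that an infusion reaction counts as a non-hematologic, non-laboratory toxicity, and that it is not treated as an immune-related AE unless the site decides so. That re-dosing is unlikely is a judgement from the safeguards; the documents give no rate, and none is assumed. DLT counts, stopping rules, sample size and analyses are untouched.

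This is a low-probability safety correction, worth making because the event is life-threatening and the remedy costs almost nothing.

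**What to change.** Let Table 5 govern. Add the clause *except Grade 3 or 4 infusion reactions, which are managed per Table 5 (permanent discontinuation)* in two places:

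1. In the DLT paragraph of Section 7.2.1, directly after the exception for immune-related AEs.
2. In the last row of Table 3.

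Naming both grades matches Table 5, which treats them alike, and also closes the small Grade 3 gap. Leave Table 5, the DLT definition and the DLT counts as they are.

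The cost is one clause in two places at the next amendment. No participants, data collection or analyses change.
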